11.1.4. Administration

Administer intravenously over 30 minutes. Do not co-administer other drugs through the same infusion line. See section 8.1 for details on pembrolizumab and administration and Section 8.1.1 for management of infusion reactions.

11.1.5. Disposal

The investigator is responsible for keeping accurate records of the clinical supplies received from Merck or designee, the amount dispensed to and returned by the subjects and the amount remaining at the conclusion of the trial.

Upon completion or termination of the study, all unused and/or partially used investigational product will be destroyed at the site per institutional policy. It is the Investigator's responsibility to arrange for disposal of all empty containers, provided that procedures for proper disposal have been established according to applicable federal, state, local and institutional guidelines and procedures, and provided that appropriate records of disposal are kept.

11.1.6. Drug interactions and Concomitant therapy

No formal pharmacokinetic drug interaction studies have been conducted with pembrolizumab.

11.1.7. Adverse Events

Common side effects (≥10% by frequency) seen with Pembrolizumab in patients with melanoma include the following:

Most Common Adverse Events in Subjects Treated with Pembrolizumab ³³

Adverse Event	${f N}$	(%)
	(Total = 2799)	
Fatigue	1044	37.3%

Version Date: 11/09/2017

Nausea	685	24.5%
Decreased appetite	630	22.5%
Diarrhea	625	22.3%
Cough	615	22.0%
Pruritus	562	20.1%
Arthralgia	504	18.0%
Rash	499	17.8%
Asthenia	362	12.9%
Pyrexia	357	12.8%

Adverse Events of Special Interest In Subjects Treated with Pembrolizumab 33

Adverse Event	N	(%)
	(Total = 2799)	
Hypothyroidism	237	8.5%
Hyperthyroidism	96	3.4%
Pneumonitis	94	3.4%
Infusion reactions	70	2.5%
Colitis	49	1.8%
Severe skin reactions	46	1.6%
Autoimmune hepatitis	19	0.7%
Adrenal insufficiency	22	0.8%
Hypophysitis	17	0.6%
Uveitis	14	0.5%
Myositis	11	0.4%
Pancreatitis	9	0.3%
Type 1 diabetes mellitus	6	0.2%
Guillain-Barre Syndrome	2	0.1%

Additional risks associated with pembrolizumab that have been identified are: Steven Johnson's Syndrome (SJS), myocarditis, and Toxic Epidermal Necrolysis (TEN)

11.2. Epacadostat

11.2.1. Dispensing of Epacadostat

An initial bulk supply of epacadostat will be provided to investigative sites prior to enrollment of the first subject. Thereafter, the site staff will contact the sponsor for re-supply of epacadostat. When dispensing to subjects, the investigator or designee will remove the appropriate quantity of epacadostat from their stock, dispense the medication, and enter the amount dispensed into the eCRF and drug accountability log.

11.2.2. Packaging and Formulation

Version Date: 11/09/2017

The drug is available at 25 mg, 100 mg, and 300 mg tablets. The drug will be packaged in high-density polyethylene bottles. All bottles will be labeled with a statement such as: "Caution: New Drug—Limited by Federal Law to Investigational Use."

11.2.3. Storage

Epacadostat should be stored at ambient conditions (15-30° C). The study drug provided in accordance with this Protocol will be kept in a secure place, and will only be supplied to subjects participating in this study.

11.2.4. Administration

Epacadostat should be taken twice daily, in the morning and evening, approximately 12 hours apart, without regard to food. If a dose is late but within 4 hours of its scheduled administration time it should be taken; if more than 4 hours have passed, the dose should be omitted and the patient should continue treatment with the next scheduled dose.

11.2.5. Disposal

The investigator is responsible for keeping accurate records of the clinical supplies received from Incyte or designee, the amount dispensed to and returned by the subjects and the amount remaining at the conclusion of the trial.

Upon completion or termination of the study, all unused and/or partially used investigational product will be destroyed at the site per institutional policy. It is the Investigator's responsibility to arrange for disposal of all empty containers, provided that procedures for proper disposal have been established according to applicable federal, state, local and institutional guidelines and procedures, and provided that appropriate records of disposal are kept.

11.2.6. Drug interactions and Concomitant therapy

See Section 8.3 for details of restricted concomitant therapy.

11.2.7. Adverse Events

Common side effects (≥10% by frequency) seen with epacadostat monotherapy in patients enrolled on a Phase 1 clinical trial:

Adverse Reactions in >10% of Patients in Phase 1 trial of Epacadostat.

Adverse Reaction	All grades (%)
General	
Fatigue	69.2%
Pyrexia	15.4
Gastrointestinal	

Version Date: 11/09/2017

Nausea	65.4
Diarrhea	26.9
Constipation	36.5
Abdominal Pain	28.8
Respiratory	
Dyspnea	25
Cough	21.2
Skin	
Rash	17.6
Metabolism	
Decreased appetite	53.8
Musculoskeletal	
Back pain	25
Nervous System	
Dizziness	11.5

12. STUDY EVALUATIONS

12.1. Screening Phase

The screening phase will be up to 28 days. Screening is the interval between the signing of the informed consent form (ICF) and the day the subject receives the first dose of treatment in the study (Cycle 1 Day 1). Informed consent must be obtained before performing any study-specific procedures not considered standard of care. Assessments that are required to demonstrate eligibility may be performed over the course of 1 or more days during this phase.

Results from the screening visit evaluations will be reviewed to confirm subject eligibility before enrollment or the administration of study drug. Tests with results that fail eligibility requirements may be repeated during the screening phase if the investigator believes the results to be in error. Additionally, a subject who fails screening may repeat the screening process 1 time if the investigator believes there has been a change in eligibility status (eg, after recovery from an infection).

See Section 13 (table 10-11) for detailed list of screening procedures.

12.2. Treatment Phase

The treatment period will continue every 21 days and may continue as long as subjects are receiving benefit from treatment and have not met any criteria for study withdrawal.

See Section 13 (Table 10 and Table 11) for detailed list and schedule of procedures while on

Columbia University Medical Center Herbert Irving Comprehensive Cancer Center Version Date: 11/09/2017

treatment.

12.2.1. Clinic Visits

During Cycle 1, patients will be seen weekly for vitals, physical exam, assessment of adverse effects, and appropriate laboratory tests and procedures (Section 13, Table 10 and table 11). Starting Cycle 2 and onward, patients will be seen on Day 1 of each cycle for vitals, physical exam, assessment of adverse effects, and appropriate laboratory tests and procedures. Patients may be seen for additional unscheduled visits as needed at the discretion of the investigator.

12.2.2. Assessment for Serotonin syndrome

Subjects will be assessed for the presence of any of the following symptoms (Table 8) of serotonin syndrome at the time points indicated in the study calendar.

Table 8: Symptoms of Serotonin Syndrome

V 1
Tremor and hyper-reflexia
Spontaneous clonus
Muscle rigidity, temperature > 38 C, and either ocular clonus or inducible clonus
Ocular clonus and either agitation or diaphoresis
Inducible clonus and either agitation or diaphoresis

12.2.3. General laboratory assessment.

See Table 11 and 12 for detailed laboratory tests and timing of these tests.

12.2.4. Schedule of Disease monitoring.

A CT scan of the chest, abdomen, and pelvis with contrast will be obtained to evaluate disease status. A scan will be obtained at baseline (within 28 days of first study drug dose), then every 6 weeks for the first 24 weeks (imaging of the area with known disease involvement only (ex: CT chest only or CT abdomen/ pelvis only) is allowed for week 6 and week 18 tumor assessments at the investigator's discretion)). After week 24, a CT chest, abdomen, pelvis with contrast will be performed every 12 weeks until disease progression, withdrawal from study, or ongoing disease control at 2 years (defined as at least stable disease at this point). For patients who achieve ongoing disease control at 2 years, treatment will be stopped and subjects will be observed with a CT scan every 12 weeks. If the patient develops disease progression during this observation time, they will have the option of restarting study treatment at that time.

Table 9: Schedule of Disease Monitoring.

	_
Baseline scan	Baseline scan within 4 weeks prior to first treatment
Weeks 1 – 24	Every 6 weeks +/- 1 week (at weeks 6, 12, 18, 24)
Weeks 25 – until disease	Every 12 weeks +/- 1 week (at weeks 36, 48, 60, 72, 84, 96,
progression	108)

Columbia University Medical Center Herbert Irving Comprehensive Cancer Center Version Date: 11/09/2017

2 years	If subjects achieve ongoing disease control at 2 years, patients
	will be taken off study treatment and observed with imaging
	every 12 weeks +/- 2 week. If the patient develops disease
	progression, the option of re-initiating study therapy may be
	agneidared

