5. STUDY DESIGN

5.1 General study design

This is a single-arm Phase 2 study to evaluate the efficacy of combined epacadostat and pembrolizumab in advanced imatinib-refractory GIST patients.

Study Intervention: All subjects will receive pembrolizumab 200 mg IV every 3 weeks and epacadostat 100 mg PO BID continuously.

Schedule of Evaluations: Subjects will have regularly scheduled study visits at the clinical site on Day 1 of every cycle (CXD1), where safety assessments, including laboratory assessments, vital signs, and physical examinations will be performed (see Section 12 for detailed study evaluations, and Section 13 for study calendar).

Response to treatment will be determined by CT scans of the chest, abdomen, and pelvis with contrast. The overall response rate for the primary endpoint evaluation will be determined by RECIST v1.1 criteria; however, clinical decision making may be made based on immune related RECIST (irRECIST) criteria to allow treatment beyond initial progression (see section 15). In patients who are unable to get a CT scan w/ contrast due to renal function (or any other reason), an MRI with and without contrast may be used instead. Imaging will be performed at the following time points:

Baseline scan	Baseline scan within 4 weeks prior to first treatment
Weeks 1 – 24	Every 6 weeks +/- 1 week (at weeks 6, 12, 18, 24)
Weeks 25 – until disease	Every 12 weeks +/- 1 week (at weeks 36, 48, 60, 72, 84, 96, 108)
progression	
2 years	If subjects achieve ongoing disease control at 2 years, patients will be taken off study treatment and observed with imaging every 12 weeks +/- 2 weeks. If the patient develops disease progression, the option of reinitiating study therapy may be considered.

Version Date: 11/09/2017

Duration of treatment: Subjects will continue treatment until confirmed radiographic disease progression, intolerable toxicity or side effects (see Section 6.6 for Criteria for Withdrawal) or ongoing disease control at 2 years. In the latter case, imaging will be performed every 12 weeks, and should the patient develop evidence of disease progression, the option of reinitiating study therapy may be considered based upon discussion with the study principal investigator.

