- 9. See section 12.2.2 for assessment of serotonin syndrome.
- 10. CT chest, abdomen, and pelvis with contrast to assess tumor status will be performed at baseline (within 28 days prior to Cycle 1 Day 1 of treatment) and then every 6 weeks (+/-1 week) during the first 24 weeks of study treatment. Imaging of the area with known disease involvement only (ex: CT chest only or CT abdomen/ pelvis only) is allowed for week 6 and week 18 tumor assessments at the investigator's discretion. After week 24, a CT chest, abdomen, pelvis with contrast will be performed every 12 weeks (+/-1 week). In patients who are unable to get a CT scan with contrast due to renal function (or any other reason), a CT chest without contrast and MRI abdomen/ pelvis with and without contrast may be used instead.
- 11. A fresh tumor biopsy will be performed at baseline within screening period, prior to C1D1 of treatment. Archived FFPE slides are not acceptable. This biopsy is mandatory. However, subjects in whom biopsy is technically not feasible or in whom would result in unacceptable risk, in the opinion of the investigator, may be exempted from the biopsy requirement with discussion with the principal investigator.
- 12. On-treatment biopsy will be obtained anytime between C2D1 and C3D1 (prior to starting cycle 3). This biopsy is mandatory. However, subjects in whom biopsy is technically not feasible or in whom would result in unacceptable risk, in the opinion of the investigator, may be exempted from the biopsy requirement with discussion with the principal investigator.
- 13. Blood for ctDNA will be collected on day $1 \pm 3d$ for cycles 1-3, and then day $1 \pm 3d$ of every other cycle thereafter. In addition, blood for PBMC collection will be collected on cycle 1 day 1 and cycle 2 day 1 (\pm 3d). See section 14.1.2 for collection instructions.
- 14. A fasting blood sample for PD analysis will be collected on Cycle 1, Day 1 (pre-dose) and Cycle 2, Day $1 \pm 3d$ (pre-dose and +2 hours (+/-30 minutes)), and at the end of treatment. See section 14.1.3 for collection instructions.
- 15. One full cycle (21 days) supply of epacadostat will be dispensed at the beginning of each subsequent cycle. Cycle 2, Day 1 epacadostat dose will be administered in clinic (for PD blood sample studies).

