15. MEASUREMENT OF EFFECT

15.1. Antitumor Effect – Solid Tumors

Initial tumor imaging must be performed within 28 days before the first dose of study treatment. For the purposes of this study, patients should be re-evaluated for response every six weeks within the first 24 weeks, then every 12 weeks for the remainder of study duration (Section 7.2.6). The study will utilize RECIST v.1.1, with responses confirmed at ≥4 weeks, for determination of the primary endpoint of ORR. The immune related RECIST (irRECIST), which is adapted for defining PD to account for the unique tumor response seen with immunotherapies (section 15), will be applied for clinical assessment of tumor response and as a basis for treating subjects beyond initial radiographic progression.

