15.5.1. Evaluation of Target Lesions by irRECIST

Tumor burden = Sum of diameter (target) + Sum of diameter (new)

Complete Response (CR): Disappearance of all target lesions. Any pathological lymph nodes (whether target or non-target) must have reduction in short axis to <10 mm.

Partial Response (PR): At least a 30% decrease in the tumor burden compared with baseline.

Progressive Disease (PD): At least a 20% increase in the tumor burden compared, taking as reference the smallest sum on study (this includes the baseline sum if that is the smallest on study), with confirmation of progression by a scan at least 4 weeks later (Note: With irRECIST, the appearance of new lesions alone is not considered progression).

Stable Disease (SD): Neither sufficient shrinkage to qualify for PR nor sufficient increase to qualify for PD, taking as reference the smallest sum diameters while on study.

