The primary endpoint of this trial is the objective response rate defined as the best response within the first 24 weeks of the start of study therapy using RECIST v1.1 criteria, and that has been confirmed at a subsequent time point (≥4 weeks).. We will use a Simon mini-max two-stage design with a target objective response rate of 20%, compared to a historical response rate of 5% with salvage tyrosine kinase inhibitor monotherapy¹⁰, and the probabilities of type I and type II error set at 0.1 and 0.2 respectively. In the first stage, 12 patients will be accrued. If less than 1 patient achieves a response among the initial 12 patients, the study will be declared negative and terminated. If at least 1 patient achieves a response, an additional 9 patients will be accrued to the second stage for a total of 21 evaluable patients. If at least 3 total patients achieve a response, that treatment will be declared positive for attaining the primary endpoint. This study design yields at least 80% power to detect a 20% response rate (compared to the null hypothesis of 5%) at a significance level of 10%. There is a 54% chance of stopping at Stage 1 if the true confirmed response rate is at most 5% (null hypothesis). Accounting for 10% dropout, we will plan to enroll a total of 23 patients.

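### A response first seen at week 12 can be confirmed on a limited-area week-18 scan that cannot exclude new lesions elsewhere; the upward bias is probably small and cheap to remove

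*Combined protocol and SAP*

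**What the plan says.** Scans in the primary window are due "Every 6 weeks +/- 1 week (at weeks 6, 12, 18, 24" (section 12.2.4, Table 9). The default is chest, abdomen and pelvis. Section 12.2.4 then adds that "imaging of the area with known disease involvement only", with chest only or abdomen/pelvis only as examples, "is allowed for week 6 and week 18 tumor assessments at the investigator's discretion". Footnote 10 of Table 10 agrees: "Imaging of the area with known disease involvement only (ex: CT chest only or CT abdomen/ pelvis only) is allowed" at the same two visits. Weeks 12 and 24 stay full.

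Section 15.1 fixes the criteria: "The study will utilize RECIST v.1.1, with responses confirmed at ≥4 weeks, for determination of the primary endpoint of ORR". Section 17.1 defines the endpoint as best response in the first 24 weeks "that has been confirmed at a subsequent time point (≥4 weeks". Neither says how much of the body the confirming scan must cover, or how an unscanned region is scored for new lesions.

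Section 5.1 states "Response to treatment will be determined by CT scans of the chest, abdomen, and pelvis with contrast". It gives an MRI substitute but no limited-area exception. The synopsis does not mention the exception either.

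**The concern.** New lesions count against a response under the criteria used for the primary endpoint. The protocol does not print the RECIST v1.1 response definitions, so this is inferred from two places. Section 15.5.1 presents the opposite rule as special to the immune-related criteria ("With irRECIST, the appearance of new lesions alone is not considered progression"), and section 15.4 treats a new lesion on FDG-PET as progression. Section 15.5.2 also requires no new lesions for a Choi response, which is a secondary endpoint. A scan of one region cannot establish that there are none elsewhere.

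The decision rests on very few patients: at least 1 response in 12 to continue and at least 3 in 21 to succeed. Scans are read at the site, section 15.8 gives response review as not applicable, and central review under section 21.9 is optional. Central review could not see an unscanned region in any case. If the full week-24 scan then shows a new lesion, no text withdraws the confirmation already made at week 18.

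**Working it through.** **Which responses are exposed.** With a window of 1 week either side, consecutive scans in the first 24 weeks are 6 − 2 = 4 to 6 + 2 = 8 weeks apart. The next scheduled scan can therefore always meet the 4-week rule.

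| Response first seen | Next scheduled scan | Extent of that scan | Exposed? |
|---|---|---|---|
| Week 6 | Week 12 | Full | No |
| Week 12 | Week 18 | May be limited | Yes |
| Week 18 | Week 24 | Full | No |
| Week 24 | Week 36 | Full | No |

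The exposed case also needs the investigator to choose a limited week-18 scan, the target lesions to remain in response, and a new lesion to arise between weeks 12 and 18 only in the unscanned region.

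**The plan's own figures** (section 17.1: null 5%, target 20%, 12 + 9 patients, stop at 0/12, success at 3/21 or more). With b(n, x, p) the binomial probability,

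P(success) = Σ over x ≥ 1 of b(12, x, p) × P[Bin(9, p) ≥ 3 − x].

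- At p = 0.05 this is 0.0804, within the 0.10 ceiling.
- At p = 0.20 it is 0.8033, which meets the stated 80%.
- Early stopping under the null is 0.95^12 = 0.540, against the stated 54%.

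The sample-size figures reproduce.

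**Chance of finishing one response short.** P(exactly 2 after continuing) = b(12,1,p) × b(9,1,p) + b(12,2,p) × b(9,0,p).

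- At 5%: 0.3413 × 0.2985 + 0.0988 × 0.6302 = 0.102 + 0.062 = 0.164.
- At 20%: 0.2062 × 0.3020 + 0.2835 × 0.1342 = 0.062 + 0.038 = 0.100.

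In those trials one false confirmation would turn 2/21 (9.5%) into 3/21 (14.3%) and a negative result into a positive one. In stage 1, one would turn 0/12 into 1/12.

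**Effect on type I error.** Let e be the absolute rate of falsely confirmed responses. The documents do not give it. Evaluate P(success) at 0.05 + e:

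| e (percentage points, assumed) | Type I error | Early stop |
|---|---|---|
| 0 | 0.080 | 0.540 |
| 0.05 | 0.082 | 0.537 |
| 0.1 | 0.084 | 0.534 |
| 0.5 | 0.100 | 0.507 |
| 1 | 0.122 | 0.476 |

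**A plausible size, by assumption only.** Suppose 40% of responses are first seen at week 12, half of those patients have a limited week-18 scan, and 5 to 10% of these develop a new lesion only in the unscanned region. Then e = 5% × 0.4 × 0.5 × (0.05 to 0.10) = 0.05 to 0.1 percentage points. Reaching e = 0.5 points would take one false confirmation for every ten true responses at the null (0.5/5).

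**The case against.** The strongest defence is that the allowance is deliberate and bounded. It is written out twice, confined to alternate visits, and bracketed by full scans at baseline, week 12 and week 24. GIST is a digestive-tract tumour, so a patient with abdominal disease would still have the whole abdomen and pelvis scanned, and typically only the chest would be missed. The route needs several conditions to hold together. All of this stands, and it is why the effect is judged small. It does not close the gap, because nothing in the plan prevents the sequence.

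A reader might take 16% and 10% as the probability of a wrong conclusion. The documents do not support that. They are the chances of having exactly 2 responses, they apply to any single misclassification, and they would have to be combined with a false-confirmation rate that is not given. A reader might also infer that the response rate is materially overstated, or that all confirmed responses are in doubt. Only responses first seen at week 12 are exposed, and false-confirmation rates of several percentage points would be implausible for this route.

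A further fair objection concerns the remedy. Deferring every such confirmation to week 24 would discard responses that held at week 18 and were lost by week 24. Power has almost no slack: losing 1% of responders takes the confirmed rate from 20% to 19.8% and power from 0.803 to 0.797. This objection stands, and the change proposed below avoids a fixed deferral.

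**Conclusion.** The gap is real but narrow. As written, a week-12 response can be confirmed at week 18 on a scan that does not exclude new lesions elsewhere, and the resulting bias in the confirmed response rate can only be upward. The documents do not determine its size. Under the assumptions shown, type I error moves from 0.080 to about 0.082 to 0.084, and it reaches the 0.10 ceiling only at 0.5 percentage points of false confirmation. The conclusion rests on the inference that new lesions count against a RECIST v1.1 response, since those definitions are not printed. The design figures are not in error.

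A minor related point: progression by a new lesion in a region left out at week 6 or week 18 would be dated at the next full scan, nominally up to 6 weeks late. This affects only PFS, a secondary endpoint.

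**What to change.** Add to section 12.2.4, Table 10 footnote 10 and section 15.1:

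*A response counts as confirmed only on a scan covering chest, abdomen and pelvis. The limited-area option does not apply at week 18 to a patient whose response was first recorded at week 12. If that scan was nevertheless limited, the next full scan is used for confirmation, and a sensitivity analysis counts the response as confirmed at week 18.*

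The MRI substitute already allowed in section 5.1 and footnote 10 should count as full coverage. The synopsis and section 5.1 should be aligned with section 12.2.4 and footnote 10, so that all four state the same exception and its limit.

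The cost is small. No visit is added, and the limited option remains at week 6 for everyone and at week 18 for everyone else. The few week-12 responders lose the shorter scan at week 18 and have the default full scan instead. Confirmation moves to week 24 only where the rule was not followed, and the sensitivity analysis shows whether that affects the result.
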